Visit 10	Day 365 (Vac 1 +12 months)	±1 month	12-month post-first study vaccination safety and immunogenicity visit
Visit 11	Day 547 (Vac 1 +18 months)	±1 month	18-month post-first study vaccination safety and immunogenicity visit
Visit 12	Day 730 (Vac 1 +24 months)	±1 month	FINAL VISIT for Groups 11-13 and Groups 16-18: 24-month post-first study vaccination safety and immunogenicity visit
Visit 13*	Day 912 (Vac 1 + 911 days)	±30 days	30-month post-first study vaccination immunogenicity visit
Visit 14*	Day 1095 (Vac 1 +1094 days)	±30 days	FINAL VISIT: 36-month post-first study vaccination immunogenicity visit

*Visits during long-term follow-up phase for participants in Groups 14 and 15 only.

Table 14: Visit Windows: Expanded Safety Cohort (Cohort 3) - One-dose Regimen and Month 12 and Month 24 Booster

VISIT	Visit Day	Window	Primary Purpose
Visit 1	Day 1	–	FIRST STUDY VACCINATION
Visit 2	Day 8	±2 days	7-day post-first study vaccination safety only visit
Visit 3	Day 15	±2 days	14-day post-first study vaccination safety and immunogenicity visit
Visit 4	Day 29	±3 days	28-day post-first study vaccination safety and immunogenicity visit
Visit 5	Day 57	±3 days	56-day post-first study vaccination safety and immunogenicity visit
Visit 6	Day 85 (Vac 1 +12 weeks)	-3/+10 days	12-week post-first study vaccination safety and immunogenicity visit
Visit 7	Day 183 (Vac 1 +26 weeks)	±14 days	26-week post-first study vaccination safety and immunogenicity visit
Visit 8	Day 365	–2 months	SECOND STUDY VACCINATION (MONTH 12 BOOSTER)
Visit 9	Day 372 (Vac 2 +7 days)	±2 days	7-day post-second study vaccination safety only visit
Visit 10	Day 393 (Vac 2 +28 days)	±3 days	28-day post-second study vaccination safety and immunogenicity visit
Visit 11	Day 547 (Vac 2 +26 weeks)	±14 days	26-week post-second study vaccination safety and immunogenicity visit
Visit 12	Day 730 (Vac 1 +729 days)	±30 days	THIRD STUDY VACCINATION (MONTH 24 BOOSTER)
Visit 13	Day 737 (Vac 3 +7 days)	±2 days	7-day post-third study vaccination safety only visit
Visit 14	Day 744 (Vac 3 +14 days)	±2 days	14-day post-third study vaccination safety and immunogenicity visit
Visit 15	Day 758 (Vac 3 +28 days)	±3 days	28-day post-third study vaccination safety and immunogenicity visit
Visit 16	Day 912 (Vac 3 +182 days)	±14 days	26-week post-third study vaccination safety and immunogenicity visit
Visit 17	Day 1095 (Vac 1 +1094 days)	±30 days	FINAL VISIT: 12-month post-third study vaccination safety and immunogenicity visit

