10.2. Discontinuation of Study Vaccine/Withdrawal from the Study

Discontinuation of Any Study Vaccine

A participant will not be automatically withdrawn from the study if he or she has to discontinue from study vaccination before the end of the study vaccine regimen.

Participants will be discontinued from vaccination for the reasons listed below. These participants must not receive any additional dose of any study vaccine but should continue to be monitored for safety and, if this does not result in safety risks for the participant, for immunogenicity (if the reason for discontinuation is not because of impaired functioning of the immune system) and/or other study procedures (eg, RTI follow-up). Additional unscheduled visits may be performed for safety/reactogenicity reasons, if needed.

In the event of questions, the investigator is encouraged to contact the sponsor:

- Anaphylactic reaction post vaccination, not attributable to causes other than vaccination
- An SAE or other potentially life-threatening (Grade 4) event that is determined to be related to study vaccine
- Any related AE, worsening of health status or intercurrent illness that, in the opinion of the investigator, requires study vaccine discontinuation
- Chronic or recurrent use of immunosuppressants (after discussion with the sponsor)
- Unblinding on the participant level that, in the opinion of the sponsor, would compromise the integrity of the data

Participants who miss a vaccination, not due to the reasons above, can receive subsequent vaccinations if, at the time of administration, the investigator determines that they are eligible to receive the vaccination according to the criteria in Section 10.3. In the event of questions, the investigator is encouraged to contact the sponsor.

Withdrawal from the Study

Each participant has the right to withdraw from the study at any time for any reason without affecting the right to treatment by the investigator. The investigator should make an attempt to contact participants who did not return for scheduled visits or follow-up. Although participants are

not obliged to give a reason for withdrawing prematurely, the investigator should make a reasonable effort to ascertain the reason(s) while fully respecting the participant's rights.

A participant will be withdrawn from the study for any of the following reasons:

- Lost to follow-up
- Withdrawal of consent
- Death
- Repeated failure to comply with protocol requirements

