2.1.1. Phase definitions

The phases in the study will be constructed as follows for all groups:

Table 1: Phase Definitions of Cohort 1, 2 and 3

Phase	Phase number	Period	Period number	Interval	
				From	To
Screening	1			00:00 of the date of signing the informed consent form ^a	One minute prior to Dose 1 on Day 1
Regimen	2	Post-Dose 1	1	Date and time of Dose 1 (Day 1)	Minimum of: 
 a) 23:59 at the date of database cut-off b) Maximum (28 days after first vaccination at 23:59, scheduled visit 4 weeks after first vaccination at 23:59) c) 23:59 at the date of last contact (for early discontinuation of the study)
Follow-Up 1	3			1 minute after end of Post-Dose 1 period	Minimum of: 
 a) 23:59 at the date of database cut-off b) One minute prior to date and time of the next vaccination c) 23:59 at the date of last contact (for completed and early discontinuation of the study)

Table 1: Phase Definitions of Cohort 1, 2 and 3

Phase	Phase number	Period	Period number	Interval	
				From	To
Regimen	2	Post-Dose 2	2	Date and time of Dose 2 (Day 57)	Minimum of: a) 23:59 at the date of database cut-off b) Maximum (28 days after second vaccination at 23.59, scheduled visit 4 weeks after second vaccination at 23:59) c) 23:59 at the date of last contact (for early discontinuation of the study)
Follow-Up 2	4			1 minute after end of Post-Dose 2 period	Minimum of: a) 23:59 at the date of database cut-off b) One minute prior to date and time of the next vaccination c) 23:59 at the date of last contact (for completed and early discontinuation of the study)
Regimen	2	Post-Boost (Month 12)	3	Date and time of Month 12 Boost	Minimum of: a) 23:59 at the date of database cut-off b) Maximum (28 days after the Month 12 boost vaccination at 23.59, scheduled visit 4 weeks after the Month 12 boost vaccination at 23:59) c) 23:59 at the date of last contact (for early discontinuation of the study)
Follow-Up Boost (Month 12)	5			1 minute after end of Post-Boost (Month 12) period	Minimum of: a) 23:59 at the date of database cut-off b) One minute prior to date and time of the next vaccination c) 23:59 at the date of last contact (for completed and early discontinuation of the study)

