5.1.3. Phase Allocation of Adverse Events

Solicited events are always allocated to the respective Post Dose period. Solicited events are allocated to the phases as described below. However, they are always allocated to the respective post-dose period and will never be attributed to a screening or follow-up phase. Time is not considered while attributing solicited AEs to phases.

For the phase allocation of unsolicited AEs, the following steps will also be followed:

Step 1: Allocation of events to the periods:

Adverse events in the SDTM database are allocated to periods based on their start date/time. If the start date/time of an event falls between (or on) the start and stop date/time of a period, the AE is attributed to that period (treatment-emergent principle).

- In case of partial start or stop dates (i.e. time and/or day and/or month and/or year missing), the events are allocated to the periods using the available partial information on start and end date; no imputation will be done. If, for instance, the AE start date only month and year are available, these data are compared to the month and year information of the periods. This rule may lead to multiplication of the event as a consequence of its assignment to multiple periods.

- In case of a completely missing end date, the date is imputed by the cut-off date of the analysis for subjects still ongoing in the study, and by the end date of the last period for subjects who discontinued or completed the trial.

- In case of a completely missing start date, the event is allocated to the first active phase (post dose 1 period), except if the end date of the AE falls before the start of the first active phase (post dose 1 period).

Step 2: Combination of events:

Overlapping/consecutive events are defined as events of the same subject with the same preferred term which have at least 1 day overlap or for which the start date of an event is 1 day after the end

date of the preceding event. Overlapping/consecutive events may be combined into one AE or not, according to the following rules:

1) If overlapping/consecutive events start in one of the following periods - Screening or intermittent follow up (i.e. non-active periods) - followed by an AE in - post-dose period (active period) - they are allocated to their respective periods and are considered as separate events.

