	>6 months post-dose	One minute after the end of the interval 57 days - 6 months post-dose	Min of: 
 • 23:59 at date of last contact (for discontinuations/completions) • 23:59 at date of DB cut-off for interim analyses

Only for participants who did not receive the 2nd dose, but who received the 3rd one.

* only applicable for cohort 1, and for participant of cohort 2 who have received a 3rd dose

SR1004 cohort 3

Dose	Interval	From	to
Post-vaccination 1	0-28 days post dose	Date time of the 1 st vaccination	Min of: 
 • 23:59 at the date of last contact (for discontinuations) • 23:59 at date of DB cut-off for interim analyses • Maximum(Date of Vaccination 1 + 28 days at 23:59 , date of scheduled visit 4 weeks after 1st vaccination at 23:59)
	29-56 days post dose	One minute after the end of the interval 0-28 days post dose	Min of: 
 • 23:59 at date of last contact (for discontinuations) • 23:59 at date of DB cut-off for interim analyses • Date of Vaccination 1 + 56 days at 23:59

	57 days - 6 months post-dose	One minute after the end of the interval 29-56 days post dose	Min of: 
 • 23:59 at date of last contact (for discontinuations) • 23:59 at date of DB cut-off for interim analyses • Maximum of (Date of Vaccination 1 + 183 days at 23:59 , date of scheduled visit 183 days post 1st vaccination at 23:59)
	>6 months post-dose	One minute after the end of the interval 57 days - 6 months post-dose	Min of: 
 • 23:59 at the date of last contact (for discontinuations) • 23:59 at the date of DB cut-off for interim analyses • 1 min prior to date time of vaccination 2
Post-vaccination M12	0-28 days post dose	Date time of the 2nd vaccination	Min of: 
 • 23:59 at the date of last contact (for discontinuations) • 23:59 at date of DB cut-off for interim analyses • Maximum(Date of Vaccination 2 + 28 days at 23:59 , date of scheduled visit 4 weeks after 2nd vaccination at 23:59)
	29-56 days post dose	One minute after the end of the interval 0-28 days post dose	Min of: 
 • 23:59 at date of last contact (for discontinuations) • 23:59 at date of DB cut-off for interim analyses • Date of Vaccination 2 + 56 days at 23:59

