	57 days - 6 months post-dose	One minute after the end of the interval 29-56 days post dose	Min of: 
 • 23:59 at date of last contact (for discontinuations) • 23:59 at date of DB cut-off for interim analyses • Maximum (Date of Vaccination 2 + 183 days at 23:59 , day 547 visit at 23:59)
	>6 months post-dose	One minute after the end of the interval 57 days - 6 months post-dose	Min of: 
 • 23:59 at the date of last contact (for discontinuations) • 23:59 at the date of DB cut-off for interim analyses

			
 1 min prior to date time of vaccination 3
Post-vaccination M24	0-28 days post dose	Date time of the 3rd vaccination	Min of: 
 23:59 at the date of last contact (for discontinuations) 23:59 at date of DB cut-off for interim analyses Maximum(Date of Vaccination 3 + 28 days at 23:59 , date of scheduled visit 4 weeks after 3rd vaccination at 23:59)
	29-56 days post dose	One minute after the end of the interval 0-28 days post dose	Min of: 
 23:59 at date of last contact (for discontinuations) 23:59 at date of DB cut-off for interim analyses Date of Vaccination 3 + 56 days at 23:59
	57 days - 6 months post-dose	One minute after the end of the interval 29-56 days post dose	Min of: 
 23:59 at date of last contact (for discontinuations) 23:59 at date of DB cut-off for interim analyses Maximum of (Date of Vaccination 3 + 183 days at 23:59 , day 912 visit at 23:59)
	>6 months post-dose	One minute after the end of the interval 57 days - 6 months post-dose	Min of: 
 23:59 at the date of last contact (for discontinuations) 23:59 at the date of DB cut-off for interim analyses

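### In the Cohort 3 AESI interval table, the post-dose-1 '>6 months' row does not stop at the Month 24 dose when Month 12 was missed, so a later event falls in two rows

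*SAP*

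**What the plan says.** The AESI part of SAP Section 5.1.3 gives each dose four basic intervals: 0–28 days, 29–56 days, 57 days to 6 months, and more than 6 months. In the Cohort 3 table:

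- The post-vaccination 1 '>6 months' row ends at the earliest of three stops. These are last contact, "23:59 at the date of last contact (for discontinuations"; the database cut-off, for interim analyses; and "1 min prior to date time of vaccination 2".
- The M12 block opens at "Date time of the 2nd vaccination" and the M24 block at "Date time of the 3rd vaccination".

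AESIs are assigned to these intervals in the same way as unsolicited events. Step 1 of that rule says that if the start falls inside a period, "the AE is attributed to that period (treatment-emergent principle".

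Protocol Section 10.2 states: "Participants who miss a vaccination, not due to the reasons above, can receive subsequent vaccinations", subject to eligibility at the time. Protocol Table 14 schedules "THIRD STUDY VACCINATION (MONTH 24 BOOSTER" at Day 730.

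Two other places in the SAP handle a skipped dose. SAP Table 1 closes each follow-up phase that precedes another dose at "One minute prior to date and time of the next vaccination". The Cohort 1/2 AESI table marks with '#' the later post-dose-1 rows for participants who skipped dose 2 but received dose 3, and stops their '>6 months' row at vaccination 3.

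**The concern.** The Cohort 3 row is tied to one numbered dose and not to whichever dose comes next. If Month 12 is missed and Month 24 is given, the stop date does not exist and nothing else closes the row at the Month 24 dose. The row then overlaps the intervals that follow that dose.

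The interval tables exist to place thrombotic and thrombocytopenic events by time since vaccination. An event a few days after the Month 24 dose would also be shown as a late event after the Day 1 dose. Such events are likely to be few, so one spurious count in a group of 135 would be noticeable. The by-interval table would also disagree with the by-phase table in the same report.

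**Working it through.** No power or sample size figure is involved. The check applies the table's rules at nominal days.

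**Inputs.** Protocol Table 14: vaccinations at Day 1, Day 365 (Month 12) and Day 730 (Month 24), final visit at Day 1095. SAP Section 5.1.3: interval bounds of dose date + 28, + 56 and + 183 days, with some bounds moved later if the matching visit is later. Events are allocated by start date.

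**Step 1: all three doses given.** Each test event falls in one interval. Day 100 is in post-vaccination 1 '57 days - 6 months'. Day 500 is in M12 '57 days - 6 months', because 365 + 56 = 421 and 365 + 183 = 548. Days 740, 770, 850 and 1000 each fall in one M24 row. The table works as intended here, and also when only Month 24 is missed.

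**Step 2: Month 12 missed, Month 24 given on Day 730, study completed.** The preceding interval ends at Day 1 + 183 = Day 184, and the '>6 months' row opens one minute later. Its three stops are last contact (discontinuations only, so not applicable), cut-off (interim analyses only, so not applicable at the final analysis) and one minute before vaccination 2 (no such date). The row has no stated end. The M24 rows end at 730 + 28 = 758, 730 + 56 = 786 and 730 + 183 = 913, and the last runs on from there.

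| Event start | M24 row | Also in post-dose-1 '>6 months' as written? | Also there if the row stops at the next vaccination? |
|---|---|---|---|
| Day 500 | none | in this row only (correct) | in this row only (correct) |
| Day 740 | 0–28 days | yes | no |
| Day 770 | 29–56 days | yes | no |
| Day 850 | 57 days to 6 months | yes | no |
| Day 1000 | >6 months | yes | no |

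Nominal overlap: 1095 − 730 = 365 days (366 counting both end days). With the visit windows in SAP Table 4 it ranges from 1065 − 760 = 305 to 1125 − 700 = 425 days. With the changed stop it is 0.

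**Step 3: do the other stops help?** No. With last contact at Day 800, events on Days 740 and 790 still fall in two rows. With an interim cut-off at Day 760, the Day 740 event does too. If the last-contact stop is read as covering completers, the row ends at the final visit and the overlap with the M24 rows remains.

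**Step 4: what is not affected.** The M24 block opens at the third vaccination regardless of the earlier rows, so its 0–28 and 29–56 day counts are right, and so are the combined 0–56 day and 0–6 month counts. The combined post-dose-1 intervals stop at 6 months and exclude the faulty row. SAP Table 1 closes the earlier phase at the next vaccination and opens a Month 24 period, so the by-phase AESI table places the event once.

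**Step 5: how many participants.** The documents give no figure. If 2%, 5% or 10% miss Month 12 but receive Month 24 (an assumption), that is 6.3, 15.8 or 31.5 of all 315, or 5.4, 13.5 or 27 of the 270 on the selected regimen. No AESI rate is given, so the expected number of duplicated events cannot be computed and may be zero.

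**The case against.** The strongest reply is that little is at stake. The analysis is descriptive, and the by-phase table, the post-Month-24 risk windows and the combined intervals are all right. The affected participants must miss Month 12 for a reason that does not end vaccination, and must give the additional consent for Month 24. All of this stands and limits the severity.

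It can also be said that Step 1 never states that one fully dated event goes into two periods; it foresees duplication only for partial dates. That is true. But Step 1 gives no rule for choosing between two intervals that both contain the start, so applying it literally yields two allocations.

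Three stronger readings are tempting, and the documents do not support them:

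- A reader might infer that a Month 24 dose given after a missed Month 12 becomes the second vaccination and is tabulated under M12. The numbering follows the scheduled slot: Protocol Table 14 ties the second and third vaccinations to Month 12 and Month 24, the notes to SAP Table 4 call the Day 365 and Day 730 slots vaccinations 2 and 3 even when missed, and the AESI blocks are labelled M12 and M24.
- A reader might infer that only the Cohort 3 table has a gap. In the Cohort 1/2 table the post-dose-1 '29-56 days' row also ends at vaccination 2 with no fallback if that dose is missed.
- A reader might borrow the Day 365 visit date as a stand-in for the missed dose. The SAP gives that substitute only for immunogenicity windows, and using it here would open post-M12 intervals for a dose that was not given.

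**Conclusion.** The row is wrong as written, and the point is minor. For a Cohort 3 participant who misses Month 12 and receives Month 24, the post-vaccination 1 '>6 months' row runs to last contact or cut-off, or has no stated end for a completer. It overlaps all M24 rows, nominally for 365 days. Each AESI starting in that time gains one spurious entry in the late post-dose-1 row and keeps its correct M24 entry. No event is lost from a risk window or credited to a dose that was not given.

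This rests on slot-based numbering, which the documents support, and on allocation by start date without a priority rule. The number of participants affected is unknown.

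**What to change.** In the Cohort 3 table, replace the vaccination 2 stop of the post-vaccination 1 '>6 months' row with the SAP Table 1 wording, "One minute prior to date and time of the next vaccination". Adding vaccination 3 as a stop when vaccination 2 was missed is equivalent and matches the '#' rows of the Cohort 1/2 table. Either change puts every test event above in exactly one interval. No separate definition of vaccination 2 and 3 is needed.

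The cost is one phrase in the SAP and a small edit to the interval derivation. Nothing changes for participants who received Month 12, and there is no analytical downside. The Cohort 1/2 '29-56 days' row could be given a fallback end in the same edit.

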5.1.4. Missing Data

Missing data will not be imputed. Subjects who do not report an event will be considered as subjects without an event. The analysis of the solicited AEs will include only documented safety data.

5.1.5. Solicited Local (Injection Site) Reactions

The analysis of local solicited adverse events, for all subjects after vaccination will include:

- Erythema
- Induration/swelling
- Pain/tenderness

5.1.6. Solicited Systemic Adverse Events

The analysis of systemic solicited adverse events for adult subjects after vaccination will include:

- Fatigue
- Headache
- Myalgia
- Arthralgia
- Chills
- Nausea
- Fever (ie, body temperature $\geq 38^{\circ}\text{C}$)

5.2. Clinical Laboratory Tests

For laboratory safety parameters, only abnormalities emerging will be tabulated by worst abnormality grade using the modified FDA table in [ATTACHMENT 1](#).

An abnormality (toxicity grade or abnormality based on normal ranges) will be considered as emerging in a particular period if it is worse than the baseline value. If the baseline is missing, the abnormality is always considered emerging. A shift from ‘abnormally low’ at baseline to ‘abnormally high’ post baseline (or vice versa) is also emerging. In case a laboratory test result is censored (no numeric value is available, but only a verbatim term) then a numeric value will be imputed by a value exceeding the cut-off value with one unit. ($<x$: subtract 1 unit from x , $>x$: add 1 unit to x ; <3.45 is imputed with 3.44).

In case no toxicity grades are defined for a test, the abnormalities (above/below normal range) will be used. In determining toxicity grades, the following rules are applied:

- worst grades/abnormalities are determined over the whole observational period for each trial period separately, including all post-baseline measurements of that period.
- The abnormalities ‘abnormally low’ and ‘abnormally high’ are considered equally important, i.e. if a subject has as well an abnormally low as an abnormally high value post-baseline, both abnormalities are shown in the tables. (This means that the sum of the percentages can be more than 100%)
- Note: as the grading scale for some parameters in the grading table has some gaps (zones where no toxicity grade definition exists), laboratory results falling in these zones will be allocated to the adjacent worst-case grade.
- If a laboratory value falls within the grading as specified in the grading table but also within the local lab normal limits, the value is considered as normal.
- HGB: for hemoglobin grades are based on both actual values and changes. Those grading will be listed separately. In addition, for the grading on the changes of HGB, the corresponding actual value should be at least grade 1.
- Only the lab values are used in determining the toxicity grades. For some lab parameters, extra clinical assessments are available to attribute grade 4 toxicity (eg. requiring hospitalization or dialysis), but these are not taken into account in the lab analysis

For the grades, no distinction will be made between test results of samples obtained under fasting and under non-fasting conditions: in case limits under fasting and non-fasting conditions differ, the limits of the conditions (fasting/non-fasting) of scheduled visits as planned in the CTP will always be used, also for samples obtained under a different condition (e.g. samples of withdrawal visits).

